10.1.3.9. Geometric mean titres (GMTs) and concentrations (GMCs)

Geometric Mean Titre (GMT) or Concentration (GMC) calculations are performed by taking the inverse logarithm of the mean of the log titre or concentration transformations. Antibody titres or concentrations below the cut-off of the assay will be given an arbitrary value of half the cut-off of the assay for the purpose of GMT/GMC calculation. The cut-off value is defined by the laboratory before the analysis and is described in the protocol.

10.1.3.10. Onset day

The onset day for an event (e.g. AE, medication, vaccination) is the number of days between the last study vaccination and the start date of the event. This is 1 for an event occurring on the same day as a vaccination (and reported as starting after vaccination).

10.1.3.11. Duration of events

The duration of an event with a start and end date will be the number of days between the start and end dates plus one day, i.e. an event that starts on 03MAR2018 and ends on 12MAR2018 has a duration of 10 days.

The duration of solicited adverse events is derived assuming that the solicited adverse event occurred continuously from the first day to the last day the event was reported, regardless of how many days the event was documented in between (i.e., $end\ date - start\ date + 1$).

10.1.3.12. Counting rules for combining solicited and unsolicited adverse events

For output combining solicited and unsolicited adverse events, all serious adverse events will be considered general events since the administration site flag is not included in the expedited adverse event CRF pages.

Multiple events with the same preferred term which start on the same day are counted as only one occurrence.

10.1.3.13. Counting rules for occurrences of solicited adverse events

When the occurrences of solicited adverse events are summarized, each event recorded as having occurred during a specific period will be counted as only one occurrence regardless of the number of days on which it occurs. Also, in the case of co-administered study vaccines, an injection site reaction recorded for a subject following multiple vaccines will be counted as only one occurrence.

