5.1.1. Rationale for the use of placebo

In order to ensure proper blinding and uniformity, placebo will be administered at Visit 1 (study Day 1) to subjects in Groups MenB and MenACWY. In addition, at Visit 4 (study Day 91), placebo will be administered to subjects in Group MenB+MenACWY while subjects in Groups MenB and MenACWY will receive MenACWY and rMenB+OMV NZ respectively.

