- After completing all prerequisite procedures prior to vaccination, vaccines should be administered by unblinded study personnel as a deep intramuscular (IM) injection, preferably into the deltoid area of the arm. To be able to efficiently distinguish local AEs after the concomitant vaccination at study Day 1 (Visit 1), the 2 injections will be separately administered into both arms. The second and third study vaccination occurring at study Day 61 (Visit 3) and study Day 91 (Visit 4) will be preferably administered into the deltoid area of the non-dominant arm. The exact anatomic location of each injection must be carefully recorded in the Medical Chart and in the eCRF (refer to Section 7.1 for detailed description of the vaccines administration procedure).

If the investigator or delegate determines that the subject's health on the day of administration temporarily precludes vaccines administration, the visit will be rescheduled within the allowed interval for this visit (refer to [Table 4](#)).

The subjects will be observed closely for at least 30 minutes following the administration of the vaccines, with appropriate medical treatment readily available in case of anaphylaxis and syncope.

As with all injectable vaccines, trained medical personnel and appropriate medical treatment should be readily available in case of anaphylactic reactions following vaccine administration. For example, epinephrine 1:1000, diphenhydramine, and/or other medications for treating anaphylaxis should be available.

In the event of any foreign particulate matter and/or variation of physical aspect being observed, do not administer the vaccine and report the issue to the manufacturer. For rMenB+OMV NZ and MenACWY vaccines the issue should be reported as a Pharmaceutical Technical Complaint. The vaccine should not be discarded until authorized by GSK. Any unused medicinal product or waste material should be disposed of in accordance with local requirements.

Detailed vaccine preparation and administration instructions will be provided to investigators in the Clinical Trials Supply Manual prior to study start.

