2. OBJECTIVES/ENDPOINTS

Objectives and endpoints are detailed in the table below:

Objectives	Endpoints
	Primary

To assess the safety and tolerability of rMenB+OMV NZ and MenACWY, when administered concomitantly or alone, in healthy subjects 16-18 years of age.
	
 • The frequencies and percentages of subjects with solicited local (i.e., injection site pain, erythema, swelling, induration) and systemic (i.e., fever [temperature $\geq 38.0^{\circ}\text{C}/100.4^{\circ}\text{F}$], nausea, fatigue, myalgia, arthralgia, headache) adverse events (AEs) during the 7 days (including the day of vaccination) following the first (Visit 1, Day 1/Month 0), the second (Visit 3, Month 2) and the third (Visit 4, Month 3) vaccination for all groups. • The frequencies and percentages of subjects with any unsolicited AEs (including all SAEs), AEs leading to withdrawal and medically attended AEs during the 30 days (including the day of vaccination) following the first (Visit 1, Day 1/Month 0), the second (Visit 3, Month 2) and the third (Visit 4, Month 3) vaccination for all groups. • The frequencies and percentages of subjects with SAEs, AEs leading to withdrawal, and medically attended AEs, throughout the study period (Day 1/Month 0 to Month 9). • The frequencies and percentages of subjects (who received rMenB+OMV NZ) with AESI throughout the study period (Day 1/Month 0 to Month 9). • Among subjects who are followed for 12 months after their last dose: 
 ○ The frequencies and percentages of subjects with SAEs, AEs leading to withdrawal, between SFU 5/Month 9 and SFU 7/Month 15 ○ The frequencies and percentages of subjects (who received rMenB+OMV NZ) with AESI between SFU 5/Month 9 and SFU 7/Month 15.

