5.5. Analysis of safety and reactogenicity

5.5.1. Analysis of safety and reactogenicity planned in the protocol

5.5.1.1. Analysis of Solicited Adverse events

All safety analyses will be performed using the Exposed set.

- Frequencies and percentages of subjects experiencing each AE will be presented for each symptom severity. Summary tables showing the occurrence of any local or systemic AE overall and at each time point will also be presented.

- Post-vaccination solicited AEs reported from Day 1 (of vaccination) to Day 7 will be summarized for the intervals Day 1-3, Day 4-7, Day 1-7 by maximal severity and by group, excluding the 30-minute measurement, which will be summarized separately. The severity of solicited local AEs, including injection-site erythema, induration and swelling will be summarized according to categories based on linear measurements as presented in [Table 6](#) below.
- Injection site pain and systemic AEs (including fever) occurring up to 7 days after each vaccination will be summarized according to “mild”, “moderate” or “severe”.
- Each solicited local and systemic AE will also be further summarized as “none” versus “any”.
- Use of antipyretics and analgesics will be summarized by frequency by type of use (prophylactic versus treatment) and percentage of subjects reporting use.
- Body temperature will be summarized by 0.5 °C increments from 38.0 °C/100.4°F up to ≥ 40 °C/104.0°F and will be broken down accordingly by route of measurement.
- Descriptive statistics (i.e., mean, median, minimum, maximum, low and upper quartiles) of the duration (in days) of solicited local (administration site) and systemic adverse events following each vaccination and overall will be provided by study group and for each solicited reaction.
- Descriptive statistics (i.e., mean, median, minimum, maximum, low and upper quartiles) of day of onset for solicited local (administration site) and systemic adverse reaction following each vaccination and overall will be provided by study group and for each solicited reaction.

Implausible measurements (for further definition see eDiary specification) will be left out of the analysis.

In the event of duplicate solicited AEs being reported both in the study eCRF and the eDiary, the Investigator's assessment will be prioritized for the main analysis.

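### The SAP text merges the two Visit 1 injection sites, so the comparison of each vaccine's local reactions with and without the other is confounded with the second site

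*SAP*

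**What the plan says.** - **Design.** Protocol 7.1: "To be able to efficiently distinguish local AEs after the concomitant vaccination at study Day 1 (Visit 1), the 2 injections will be separately administered", one in each arm. It adds: "The exact anatomic location of each injection must be carefully recorded in the Medical Chart and in the eCRF". Under Protocol 5.1.1, "placebo will be administered at Visit 1 (study Day 1) to subjects in Groups MenB and MenACWY", so every group has two injection sites at Visit 1.
- **Objective.** The first primary objective (SAP 2) reads "To assess the safety and tolerability of rMenB+OMV NZ and MenACWY, when administered concomitantly or alone". Solicited local AEs in the 7 days after each vaccination are a named endpoint.
- **Counting rule.** SAP 10.1.3.13 is introduced by "When the occurrences of solicited adverse events are summarized" and says that, for co-administered study vaccines, "an injection site reaction recorded for a subject following multiple vaccines will be counted as only one occurrence". Protocol 7.1 lists placebo among the study vaccines, so the rule also covers the Visit 1 pairs that contain placebo.
- **Tables.** SAP 5.5.1.1: "Summary tables showing the occurrence of any local or systemic AE overall and at each time point will also be presented". Its other solicited-AE summaries are by group, vaccination, time interval and severity. If a participant has several local measurements on one day, only the worst is analysed. Protocol 10.3.4 gives no split by site or product either.
- **No override.** SAP 10.1 applies these standard rules together with the study-specific rules of Section 9, and Sections 9.1 and 9.2 are both marked not applicable.

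**The concern.** The design separates the two sites for a stated purpose, and the analysis text then joins them again. Co-administration occurs only once, at Visit 1 in Group MenB+MenACWY. Two comparisons there bear directly on tolerability with versus without the other vaccine: the rMenB+OMV NZ site in Group MenB+MenACWY against Group MenB, and the MenACWY site in Group MenB+MenACWY against Group MenACWY. Once the sites are merged, each comparison also contains a difference in what went into the other arm, active vaccine against saline.

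This can mislead in both directions. Co-administration can appear to raise local reactions when neither vaccine has changed the other's. A real rise at one site can also be hidden by reactions at the other. Safety comparisons are descriptive and untested, so the tabulated percentages are the whole result for this objective.

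**Working it through.** The plan gives no local reaction rate, so it has no figure of its own to reproduce. All rates below are assumptions, used only to show how a merged count behaves.

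**Inputs**
- Visit 1 pairs (Protocol Table 10): rMenB+OMV NZ with MenACWY; rMenB+OMV NZ with placebo; MenACWY with placebo.
- Assumed site rates, taken as unaffected by the other injection: b = 60–80% (rMenB+OMV NZ), c = 30–50% (MenACWY), p = 10–30% (placebo).
- Merged rate for sites with rates x and y: 1 − (1 − x)(1 − y) if independent, max(x, y) if they overlap completely.

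**Step 1: difference with no interaction**

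Under independence, Group MenB+MenACWY exceeds Group MenB by (1 − b)(c − p), and exceeds Group MenACWY by (1 − c)(b − p). Under complete overlap the excesses are max(b, c) − max(b, p) and max(b, c) − max(c, p).

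| Comparison | Smallest | Largest |
|---|---|---|
| vs Group MenB | 0, under complete overlap (b exceeds c and p), or whenever c = p = 0.3 | b = 0.6, c = 0.5, p = 0.1, independent: 0.80 − 0.64 = +16 points |
| vs Group MenACWY | b = 0.6, c = 0.5, complete overlap: 0.60 − 0.50 = +10 points | b = 0.8, c = 0.3, complete overlap: 0.80 − 0.30 = +50 points |

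The difference at each vaccine's own site is zero in every case.

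**Step 2: a real effect**

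Hold the rMenB+OMV NZ site at 80% and let the MenACWY site rise from 40% to 60% because of co-administration.
- Independent: 1 − 0.2 × 0.6 = 88% becomes 1 − 0.2 × 0.4 = 92%, a rise of 4 points.
- Complete overlap: 80% stays at 80%, a rise of 0 points.

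A 20-point change at the site appears as 0 to 4 points in the merged count.

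**Step 3: one merged figure, many patterns**

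With independent sites, a merged 88% arises from rMenB+OMV NZ/MenACWY rates of 80/40, 70/60, 60/70 or 40/80. The merged figure alone does not identify the site rates.

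**Step 4: what a split would give**

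With 315 per group (the planned enrolment, assumed all to have diary data), the 95% half-width for a site-level difference is 1.96 × √(2r(1 − r)/315). At r = 80% this is 6.2 points, and at r = 40% it is 7.7 points.

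**The case against.** - **Standard rule.** SAP 10.1.3.13 is a sponsor-wide rule against double counting and does not forbid a by-site table. This stands. A reader might infer that the SAP rules such a table out; it does not. It specifies none.
- **Unseen table list.** SAP 10.2 puts the tables and their layouts in a separate document, which may already hold by-site tables. This stands.
- **Single injections later.** Visits 3 and 4 have one injection each, so each product given singly can be read there: rMenB+OMV NZ at Visit 3 in all groups, and MenACWY at Visit 4 in Group MenB. A reader might infer that local tolerability of each vaccine alone cannot be read at all. The documents do not support that. These visits come later in the sequence, however, and supply no co-administered comparison.
- **Endpoint as defined.** The safety endpoint is the percentage of subjects by group and vaccination, and the merged count delivers it. That is correct, but the objective above it concerns each vaccine given with or without the other.
- **Real burden.** A higher any-site rate after two active injections is a real cost of the visit. A reader might take the whole excess as an artefact; that is wrong. The merged rate measures per-visit burden, but it does not show whether one vaccine changes the other's local reactions.
- **Consequences.** Study success (Protocol 4) rests on immunogenicity alone, so no pre-specified decision depends on this.

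**Conclusion.** The point holds for the summaries specified in the SAP text. As written, they merge the two Visit 1 sites, and the with-versus-without comparison of each vaccine's local reactions at that visit is confounded with the second site, active or saline.

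The size is illustrative. Under the assumed rates and the two extremes of association between sites, the merged count shows 0 to +16 points against Group MenB and +10 to +50 against Group MenACWY with no interaction, and only 0 to 4 points for a real 20-point rise at the MenACWY site. Actual values depend on rates and within-subject correlation that the documents do not give.

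A reader might infer that the information is lost. The documents do not show this: injection locations are recorded, all same-day measurements are listed, and the table list has not been seen. The purpose stated in Protocol 7.1 implies capture of reactions by arm, but neither document states that the eDiary does so.

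**What to change.** In SAP 5.5.1.1 and 10.1.3.13, state that:

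1. Visit 1 solicited local AEs are tabulated within each group by injected product (rMenB+OMV NZ site, MenACWY site, placebo site).
2. The merged any-site row is kept and labelled as the per-visit burden.
3. For the by-site rows, the one-occurrence rule and the worst-measurement-of-the-day rule apply within site.

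The split should follow the product and the recorded injection location, not left or right arm: Protocol Table 10 places MenACWY on the right in Group MenB+MenACWY and on the left in Group MenACWY.

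If the separate table list already contains these tables, a sentence aligning the SAP with it is enough. Otherwise the cost is one extra set of descriptive tables, with no new visits, subjects or tests. This assumes that the eDiary records local reactions by arm, which the sponsor should confirm first. If it does not, the SAP should say that the split is unavailable and that the merged Visit 1 rates do not isolate the effect of one vaccine on the other's local reactions.

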10.1.4. Display of decimals**10.1.4.1. Percentages**

Percentages and their corresponding confidence limits will be displayed with:

- no decimals when there are fewer than 50 subjects in each tabulated group
- one decimal when there are at least 50 subjects in at least one tabulated group

- Exceptions will be made for percentages that are not 0% or 100% but appear as 0% or 100% due to rounding. For these specific cases the number of decimals will be increased until the displayed value is no longer 0% or 100%. Examples are given in the following table.

n/N	Displayed percentage
10/45	22%
1/45	2%
10/55	18.2%
1/55	1.8%
1/300	0.3%
1/3000	0.03%
1/30000	0.003%
299/300	99.7%
2999/3000	99.97%
29999/30000	99.997%

- The display of additional decimals for values close to 0% or 100% will be applied only to point estimates and not confidence limits, which can be rounded and displayed as 0% or 100%.
- Values of exactly 0% or 100% will be presented with no decimals regardless of the number of subjects per tabulated group.

10.1.4.2. Differences in percentages

Differences in percentages and their corresponding confidence limits will be displayed with one more decimal than the maximum number used to display the individual percentages, for example the difference between two percentages displayed with one decimal will be displayed with two decimals.

10.1.4.3. Demographic/baseline characteristics statistics

The mean, median, and standard deviation for continuous baseline characteristics (height, weight, body mass index (BMI), pre-vaccination body temperature) will be presented with one decimal.

The minimum and maximum values and quartile values (if required) will be presented with the same number of decimals as the observed values.

The maxima and minima of transformed height variables will be displayed with no decimals.

The maxima and minima of transformed weight variables will be displayed with no decimals with the exception of values are below 10kg where one decimal will be displayed.

The maximum and minima of transformed body temperatures will be displayed with one decimal.

10.1.4.4. Serological summary statistics

The number of decimals used when displaying geometric mean titers (GMT) or concentrations (GMC) and their confidence limits is shown in the following table:

GMT or GMC value	Number of decimals to display
<0.1	3
≥0.1 and <10	2
≥10 and <1000	1
≥1000	0

When multiple categories of GMT or GMC values are present in the same table, the number of decimals displayed should match that of the smallest category (i.e. the one with the higher number of decimals). For example, if GMT or GMC values of <0.1 appear in the same table as values of ≥0.1 and <10, 3 decimals should be displayed for both.

GMT or GMC ratios and their confidence limits will be displayed with 2 decimals regardless of the actual values.

10.1.5. Statistical methodology

10.1.5.1. Exact confidence intervals around proportions

The exact confidence intervals around within-group proportions are derived using the method of Clopper and Pearson [[Clopper](#), 1934].

10.1.5.2. Standardized asymptotic confidence intervals around differences in proportions

The standardized asymptotic confidence intervals around differences in proportions are derived using the method of Miettinen and Nurminen [[Miettinen](#), 1985].

10.1.5.3. Adjusted GMT or GMC ratios

The CI for GMC ratio and adjusted GMT will be obtained using an ANOVA model on the logarithm transformed titers. The ANOVA model will include the vaccine group as the fixed effect (3 groups) and the country effect. The GMC ratio and their 95% CI will be derived by exponential transformation of the corresponding group contrast in the model.

When between-group GMT or GMC ratios are computed and adjusted for two-level categorical co-variables, these co-variables should be included as dummy continuous variables in the SAS procedure. It should also be clear whether the model is limited to the data from some groups.

10.1.5.4. Vaccine efficacy

NA

10.2. TFL TOC

The Table Figure Listing (TFL) Table Of Content (TOC) which itemizes the planned list of TFL and their associated lay-out is developed as a separate document.

